4.3 Cohort II: Emulated Delivery Cohort

The BgRT product design is such that when used to guide treatment delivery, the hardware instructions for the linear accelerator, gantry, and MLCs are determined during each fraction based upon the dynamic input of PET LTS images on that day. Therefore, each fraction of treatment delivery is expected to utilize different hardware instructions than the others. Nonetheless, each of these delivered variations and their individual dose volume histograms (DVH_{Delivered}) should be reflected in the approved BgRT plan, which represents the spectrum of delivery possibilities (within an allowed threshold of variation) in the bounded dose volume histogram (bDVH).

The chief objective of this cohort is to confirm that the machine-deliverable fluence generated by applying the BgRT firing filter to PET LTS images obtained at the time of a radiotherapy delivery does in fact result in an anatomic dose distribution that is consistent with the approved BgRT plan. A secondary objective is to extend this analysis by also confirming that the linear accelerator subsystem hardware is able to deliver the received machine instructions. Importantly, this investigation comprehensively emulates and assesses (without actually delivering the radiation therapy to the patient) the entire end-to-end BgRT workflow from simulation to treatment planning to, finally, dose delivery. This design also provides an opportunity to assess imaging, workflow, and the toxicity, if any, associated with multiple administrations of FDG.

To do this, 8 to 22 subjects dispositioned to undergo conventional SBRT for a single bone tumor or a single lung tumor will be enrolled. As noted previously, patients with multiple metastases can be accrued but the investigation will focus only one targeted lesion per patient. For each patient, RMRS PET collections will be added to the SBRT workflow at 3 timepoints representing the steps when the RMRS PET subsystem would be utilized during the BgRT workflow. Specifically, these timepoints will include a RMRS PET imaging-only session prior to the start of SBRT delivery that will be used to create a BgRT plan as well as RMRS PET collections before the first and final fractions of their planned course of SBRT (*Figure 6*). A single comparison third-party diagnostic PET/CT image will also be obtained (utilizing the same FDG injection) on the day of the final fraction.

The two fractional timepoints are selected because they will capture any day to day PET variations as well as potential interference on the tumor PET signal arising from the radiotherapy itself. A PET collection prior to the start of the treatment course will not be influenced by the SBRT treatment itself, whereas the PET collection preceding the final fraction will be subject to the full impact of SBRT on the tumor PET profile.

In order to emulate BgRT delivery, each of these fractional PET collections will consist of two phases:

- Short-duration PET collection that corresponds to the duration of a PET PreScan Evaluation
- Long-duration PET collection that corresponds to the duration of an active BgRT delivery fraction

The long-duration PET collection data mimics RefleXion LTS PET image acquisition during live BgRT and will be used to determine the hardware instructions that would be transmitted to the RefleXion delivery hardware (linear accelerator, gantry, MLC, etc.) based upon the algorithmic interaction between the incoming LTS images and the approved BgRT treatment plan.

[figure not shown]

Figure 6. Cohort II Patient Encounters

Primary Objective: The quality of each specific instance of emulated BgRT dose delivery will be validated in two ways. Firstly, the dose distribution resulting from the hardware instructions triggered by fraction timepoint LTS images will be modeled *in silico* on the patient's CT anatomy. This radiotherapy dose distribution will be checked against the expectations of the approved BgRT plan. As such, the primary endpoint is the percent of radiotherapy fractions where the emulated BgRT dose distribution *in silico* is shown to be consistent with the approved BgRT treatment plan (i.e., 95% of DVH_{Delivered} points for the BTZ and OARs fall within the bounded DVH of the approved BgRT plan).

[figure not shown]
Secondary Objectives: The second test of dose distribution quality is to confirm that the machine instruction-set generated by the BgRT algorithm can be effectively and accurately carried out by the linear accelerator hardware to deliver the intended dose and distribution.

To that end, the fluence resulting from the hardware instruction set will be delivered into a physical phantom in order to emulate delivery during BgRT. The dose and distribution measured in the phantom will be judged against *in silico* delivery of the same instruction set to a digital facsimile of the phantom, as per standard physics quality assurance methodology.

As such, the first secondary endpoint will be the following:

1. Percent of fractions where there is concordance between the physical and digital phantoms of emulated BgRT delivery derived from human subject PET emissions. Concordance is defined as a standard gamma index with a goal that 90% of pixels meet the 3mm/3% deviation standard.

Collectively, these primary and secondary analyses emulate end-to-end BgRT delivery insofar as they enable visualization of anatomic dose distributions resulting from varying PET LTS conditions and confirm quality assurance and delivery of those dose distributions by the linear accelerator hardware. In this way, these analyses address the known limitation of human subjects research in radiotherapy device validation (see section 1.5), which is that dose distributions are not directly measurable *in vivo*.

[figure not shown]

Figure 7. Physical and Dosimetric Validation of BgRT Plan Delivery Based upon Human-Subject Derived PET Data on the RefleXion System

To reflect clinical conditions, these analyses of BgRT dose distribution are necessarily limited to those fractions where BgRT would have been delivered in practice. Therefore, a dose distribution is evaluable for the primary endpoint if, preceding the long-duration PET collection, (1) an acceptable BgRT plan was approved and (2) the PET PreScan evaluation delivered a "Pass" signal. In order to obtain a total of 16 evaluable dose distributions for assessing delivery quality in Cohort II, a minimum of 8 subjects (4 bone tumors and 4 lung tumors) and up to 22 subjects can be accrued. For an enrolled subject, if a PET PreScan delivers a "Fail" signal prior to long-duration PET collection, then the investigator can choose to repeat FDG administration at a subsequent treatment fraction for that subject (which again reflects clinical practice). If a data point is ultimately non-evaluable, then an additional patient with the same anatomic type of tumor can be accrued. Once a total of 16 evaluable dose distributions are acquired, Cohort II accrual will stop.

The next two secondary endpoints assess the imaging performance of the PET PreScan. The first of these endpoints seeks to assess the inter-observer agreement for the localization decision made after each RMRS PreScan. A positive or negative decision on the PET PreScan will be indexed against current standard of care for radiotherapy tumor localization: CT-based localization. As such, whether the tumor PET signal is within the BTZ – which is a rigid volume defined on and registered to the patient's CT anatomy – will underpin this determination. The localization decision made by the site investigator will be assessed against an agreement standard made by a panel of independent reviewers using the same RMRS PreScan images with the overlaid BTZ:

2. Percent of cases where there is an agreement between a site investigator and the agreement standard for the BgRT PET PreScan localization decision (overall percent agreement). Positive percent agreement and negative percent agreement will also be reported.

The next imaging secondary endpoint seeks to validate the qualitative visualization of the tumor and OARs on the PreScan against an established reference standard. To establish this concordance, a third-party diagnostic PET/CT scan following the RMRS PET acquisitions obtained prior to the last fraction.

3. Percent of cases where there is concordance of a positive localization decision between the shortduration PET PreScan and a third-party diagnostic PET/CT scan (positive percent agreement). Overall percent agreement and negative percent agreement will also be reported.

Details of these two imaging analyses are described in section 6.3.8 and 6.3.9. Of note, these endpoints will not be limited to only those cases that are evaluable for the primary endpoint. Nonetheless, interpretation of the results of this analysis should bear in mind that the clinically meaningful localization decisions are the positive ones because they would prompt BgRT external beam delivery; negative localization decisions at the RMRS PET PreScan would result in aborting BgRT delivery in clinical practice.

A fourth secondary endpoint is to measure toxicity arising from multiple administrations of FDG. As described in detail in the IB, the theoretical risk is minimal given first principles of radiation exposure and reassuring animal and human studies of very high-dose FDG administrations. This secondary endpoint will seek to further confirm safety by assessing the organs most likely to be affected by repeat FDG administrations:

4. Safety of multiple FDG administrations and toxicity rates of bladder and bone marrow assessed by complete blood count, urinalysis and AEs specific to bladder and bone marrow determined by Common Terminology Criteria for Adverse Events (CTCAE) v5 at 72±24 hours after final FDG injection.

Finally, characterization of the different steps in the workflow and the robustness of the PET Evaluation pre-delivery will be assessed to better characterize RefleXion system functioning. This data will be collected for all enrolled subjects regardless of the evaluability of their BgRT dose distributions:

- 5. Workflow characterization:
 - a. Percent of PET imaging sessions at RRFD that meet BTZ activation concentration threshold for BgRT (5 kBq/ml)
 - b. Percent of PET imaging sessions that lead to acceptable BgRT plans, with acceptability based upon meeting user-defined coverage goals for tumor targets and avoidance goals for OARs
 - c. Percent of approved BgRT plans that go on to pass physics quality assurance as defined by 90% of pixels meet the 3mm/3% deviation standard.
 - d. Percent of PET PreScan Evaluations on the day of fraction delivery that elicit a "Pass" signal.

For each of these conversion assessments, the constituent metrics underling the outcomes will be recorded. For example, the underlying measurements for the PET PreScan Evaluation (i.e., Activity Concentration, NTS level, predicted DVH, predicted 3D dose distribution, and calculated agreement between the predicted DVH and bounded DVH) will be recorded for each assessment.

Additional exploratory analysis for Cohort II may include pairwise dosimetric comparison of the BgRT and SBRT plans for each lesion. When additional time-paired third-party images are available, they may be compared to RMRS PET images and a qualitative assessment may be performed.

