2.2.2 Secondary Objective

To emulate and confirm deliverability of the fluence associated with the BgRT dose distribution generated from LTS PET images obtained at the time of treatment delivery as well as to assess imaging, process and safety characteristics of the end-to-end workflow.

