For physical validation, the emulated fluence (dose) from the primary endpoint analysis is utilized. RefleXion offline tools will convert the machine instructions into a deterministic radiotherapy (RT) plan. Deliverability of the plan is confirmed by comparing its resultant dose distribution, measured in a physical phantom, to a model of plan delivery in a digital representation (CT image) of the same phantom. A standard gamma index will be utilized for this confirmation with a goal that 90% of the pixels meet the 3mm/3% deviation standard (see cohort II secondary endpoint 1). The ArcCHECK platform will be utilized to perform this assessment.

Table 2: Cohort II - Study Event Schedule

	Screening & Baseline ¹	Planning / PET Imaging-only session (within 7 days prior to the first fraction of SBRT)	First Fraction of SBRT	Last Fraction of SBRT	Follow-Up (72±24 hours after final FDG administrati on)
Informed Consent ²	x				
Demographics, Medical History & Physical Exam	х				
CBC	x				x
СМР	x				x
Blood glucose	x	x	x	х	x
Urinalysis	x				x
ECOG performance status	x				x
Pregnancy test ³	x				
FDG injection ^₄ (RRFD based on Cohort I)		x	x	х	
RMRS PET w/ kVCT localization ^{4,5}		x	x	х	
Third-party diagnostic PET/CT ^{4,5}				х	
AE assessment ⁶	x	x	x	х	x

¹Baseline Assessments should be completed within 14 days prior to the PET Imaging-only session

²Informed consent is not considered a baseline assessment and has no requirement to be completed within a specific time window from study visits

³Women of child-bearing potential only, if applicable within 14 days prior to the initiation of the study scans.

⁴At the last SBRT fraction timepoint, if the third-party PET scan cannot be initiated within 180 minutes of original FDG injection, then the third-party scan can be completed with a separate FDG injection 24 to 96 hours after the initial FDG injection.

⁵Images should be de-identified before submitting to RefleXion Medical. Type of RMRS PET acquisition (shortduration, long-duration, etc.) as per written protocol.

⁶AEs to be assessed using Common Terminology Criteria for Adverse Events (CTCAE) v5. In Cohort II, directed grading for bladder and bone marrow toxicity will be completed at baseline and 72±24 hours after final FDG administration.

6.3.8 Schema for Cohort II Secondary Endpoint #2: RMRS PreScan Image Inter-Observer Localization Agreement

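### Section 6.3.7 converts the LTS-derived instructions before the phantom test, and secondary endpoint 1 as described does not check that conversion

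*Combined protocol and SAP*

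**What the plan says.** The secondary objective in section 2.2.2 is "To emulate and confirm deliverability of the fluence associated with the BgRT dose distribution generated from LTS PET images". Section 4.3 gives the aim of the second test as to "confirm that the machine instruction-set generated by the BgRT algorithm can be effectively and accurately carried out by the linear accelerator hardware". It then describes the two sides of the comparison. On the physical side, "the fluence resulting from the hardware instruction set will be delivered into a physical phantom in order to emulate delivery during BgRT". On the reference side is in silico "delivery of the same instruction set to a digital facsimile of the phantom, as per standard physics quality assurance methodology". Section 4.3 mentions no conversion.

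Section 6.3.7 describes the procedure. For the primary endpoint, the machine instructions calculated from the LTS images are modelled on the patient's CT, again with no conversion described. For the phantom test the paragraph starts from the fluence of the primary analysis and continues: "RefleXion offline tools will convert the machine instructions into a deterministic radiotherapy (RT) plan". After that, "Deliverability of the plan is confirmed by comparing its resultant dose distribution, measured in a physical phantom", and the comparator is given as "to a model of plan delivery in a digital representation (CT image) of the same phantom". The criterion is a 3 mm/3% gamma index with a goal of 90% of pixels. The only safeguard stated for the software is that the sponsor will supply validated tools, training and procedures.

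**The concern.** In the phantom paragraph of 6.3.7 the only plan named is the deterministic plan that comes out of the conversion. Read plainly, that plan is what is measured and also what is modelled. The instruction set that produced the primary-endpoint dose then appears on neither side. If the conversion changed the fluence, for example by a scale factor, an offset or lost partial fluences, both sides would carry the same change and gamma would not respond to it.

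Within Cohort II, secondary endpoint 1 is the only measurement of physically delivered LTS-derived fluence. The plan QA in workflow item 5c tests the approved plan, using planning PET and a static target (section 1.3.2). Section 4.3 says the primary and secondary analyses together confirm that the hardware delivers the dose distributions arising from the LTS images. If the conversion is not verified, the endpoint shows that a converted plan can be delivered as modelled. The step from there to the dose scored in the primary endpoint is left as an assumption.

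**Working it through.** **The plan's own figure.** Section 13.1.2 gives 0.811 for at most 1 inconsistency in 16 at a true rate of 5%. Check: 0.95^16 + 16 × 0.05 × 0.95^15 = 0.4401 + 0.3706 = 0.8108. The other four entries also reproduce (0.0033, 0.0261, 0.1407, 0.5147). This figure concerns the primary endpoint and does not bear on the present point. Secondary endpoint 1 is descriptive, with no power or margin to recompute.

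**The comparison in symbols.** Let I be the LTS-derived instruction set, C the conversion, H the dose measured after hardware delivery to the phantom, and M the modelled dose in the digital phantom.

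- Section 4.3, read literally: H(I) against M(I).
- Section 6.3.7, read literally: H(C(I)) against M(C(I)).
- Primary endpoint: a modelled dose from I on patient CT.

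The first two coincide if C(I) = I. If C(I) differs from I but can still be delivered, the difference enters both terms of the 6.3.7 comparison and drops out. Nothing described compares C(I) with I. Detecting such a difference needs H(C(I)) against M(I).

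**Illustration of size (assumptions, not trial estimates).** The documents give no dose arrays, so the dose shapes are assumed:

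- square fields of 30, 50 and 70 mm with error-function edges of sigma 2, 3, 5 and 8 mm (12 shapes);
- Gaussian doses of sigma 10, 15 and 20 mm (3 shapes);
- a circular dose 1/(1 + exp((r − 18)/4)), r in mm (1 shape).

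Settings: 2D, 0.5 mm grid, global 3%/3 mm gamma, 10% low-dose cut, perfect hardware. This does not model the ArcCHECK geometry. A point passes if the minimum of (dose difference / 3% of maximum)² + (distance / 3 mm)² is at most 1.

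| Assumed conversion error | Passing, converted plan on both sides | Passing, against unconverted instructions | Shapes below 90% |
|---|---|---|---|
| 2% scaling | 100% | 100% | 0 of 16 |
| 2 mm or 3 mm offset | 100% | 100% | 0 of 16 |
| 5% scaling | 100% | squares 29–98%, circular 93%, Gaussian 98–99% | 10 of 16 |
| 10% scaling | 100% | squares 18–92%, circular 83%, Gaussian 91–96% | 12 of 16 |
| 4 mm offset | 100% | 56–83% over all shapes | 16 of 16 |

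The middle column is 100% by construction. The next column shows that the alternative reference responds to errors beyond tolerance, reliably for the offset and only for some shapes for the scaling.

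**The case against.** Several things can fairly be said for the plan.

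- **Section 4.3 also puts one object on both sides.** It never uses the word unconverted. A reader might infer that 4.3 prescribes an unconverted reference which 6.3.7 contradicts. The text does not support that: the sections are compatible if the conversion is exact. What remains is that this condition is neither stated nor checked.
- **Modelling and measuring the same plan is the protocol's QA method** (sections 1.3, 1.3.2, 1.5 and 6.2.2), and it isolates hardware performance. Replacing the reference outright would mix software and hardware error in one result. This stands, and it is the reason to keep both comparisons.
- **Section 6.3.7 starts from the primary-endpoint fluence, calls the tools validated and sends machine log files to the sponsor.** That fixes the input to the conversion. It does not describe a check of the output against the input for each fraction.
- **Figure 7, the User Manual and the tool validation are not available here.** A conversion check may exist elsewhere. If so, 6.3.7 should cite it.
- **The endpoint is descriptive, and the trial supplements separate phantom work** (sections 1.5, 4.1 and 13.1.2). This limits the consequence but does not remove the stated deliverability objective.

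**Conclusion.** The point holds as a gap in the described procedure. On the plain wording of 6.3.7, a conversion error that still yields a deliverable plan would not lower secondary endpoint 1, so the endpoint would not by itself confirm delivery of the fluence scored in the primary endpoint, as 2.2.2 intends. This rests on reading the plan in that paragraph as the converted plan, and on no per-fraction check being specified elsewhere.

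Three stronger conclusions that a reader might draw are not supported:

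- **The endpoint is blind to every conversion error.** An error that makes the plan undeliverable, or that hardware and dose model handle differently, could still fail gamma.
- **A conversion error occurs or is likely.** Nothing in the documents shows this.
- **The primary result is compromised.** It is computed from the machine instructions on patient CT, and neither it nor the 16-distribution calculation changes.

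The size is illustrative only. The 4 mm offset result was consistent over the shapes tried; the 5% scaling result was not. Errors within tolerance pass under either reference.

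**What to change.** In 6.3.7, also compute the digital-phantom dose from the unconverted LTS-derived machine instructions, the same set used for the primary endpoint. Score secondary endpoint 1 (measured dose, 3%/3 mm gamma, 90% of pixels) against that reference. Report the converted-plan comparison alongside it for every fraction, with identical gamma settings. A fraction that passes against the converted plan and fails against the unconverted instructions points to the conversion. One that fails against the converted plan points to the hardware or the dose model. Reword 4.3 and 6.3.7 so that both name the object delivered and the object modelled. If conversion accuracy is already verified in another document, cite it.

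The cost is about 16 extra forward dose calculations, one per evaluable distribution, and no extra patients, scans or beam time. This assumes that the in silico tool, described only for patient CT, can also use the phantom CT; the sponsor should confirm that. The reported pass rate may be lower than with the converted plan on both sides.

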5. STUDY POPULATION

- 5.1 Selection Criteria
- 5.1.1 Inclusion Criteria
- 1. Age greater than 21 years
- 2. A new or prior diagnosis of biopsy-proven cancer with a solid tumor (non-hematologic, non-lymphoma)
- 3. At least one active tumor in the bone or lung which is either the primary tumor or metastatic lesion determined either by biopsy or imaging suspicious of active disease
- 4. Target tumor size ≥2cm and ≤5cm

- Target lesion in the bone or lung that is discrete and assessed by investigator to be FDG-avid (i.e. SUV_{max}≥6 on third-party diagnostic PET/CT performed within 60 days with no new intervening oncologic therapies)
- 6. ECOG Performance Status 0-3
- 7. Must have completed any other oncologic therapies at least 15 days prior to planned start of study procedures (preferably 30 days) and must have no plans to initiate systemic therapy until after study follow up is complete -OR- must be recorded by physician to have an active candidate lesion that is unresponsive to ongoing systemic therapy
- 8. Females of childbearing potential should have negative urine or serum pregnancy test within 14 days prior to initiation of study scans.
- 9. Demonstrate adequate organ function:
 - a. Absolute neutrophil count (ANC) > 1,500 /mcL
 - b. Platelets > 50,000 / mcL
 - c. Hemoglobin > 8 g/dL
 - d. No gross hematuria
- 10. For Cohort II only: Patient is dispositioned to undergo SBRT to a bone or lung tumor

